5.2 Study Visits and Assessments

A summary of this ancillary study's assessments is provided in the table below. Given that this is a pilot study, we will allow for flexibility for the administration of some assessments at visits, as long as these changes do not impede the scientific interpretation.

Assessment	Baseline	4 Weeks	8 Weeks	12 Weeks
Fecal Sample	X			X
Suicidal Ideation (via P4SS)*	X	X	X	X
Depression Severity (via CES-D)	X	X	X	X
3-Day Diet Record*	X	X	X	X
Relevant Symptoms*	X	X	X	X
Positive and Negative Affect	X	X	X	X
Compliance*		X	X	X

* Reflects that this measure is also a part of the parent study

The parent study consists of up to 6 study visits: a screening visit, a baseline visit, 3 mid-point visits, and a final follow-up visit. The ancillary study adds additional assessments to the baseline visit, 2 of the 3 mid-point visits, and the follow-up visit in week 12. Information on the study procedures at the study visits related to the ancillary study is outlined below.

Informed Consent: In order to participate in this study, all interested and eligible participants will be required to provide informed consent. They will be given ample time to ask any questions about the study. A trained research staff will answer any questions and if the individual is interested in participating in the study, they will be offered to sign the informed consent form. When the staff is confident that the participant is completely

familiar with the document and understands all the aspects of the informed consent form, it should be signed by the participant in the presence of the staff member, and should then be signed by the staff member. All consent forms will be double checked to make sure they are properly signed and dated. Copies of completed consent forms will be given to the participant and the original signed document will be kept on file at the Hinda and Arthur Marcus Institute for Aging Research. As a part of the informed consent process, potential participants will be clearly informed that this intervention is not a treatment option for depressive symptoms or depression, but rather studying feasibility of a dietary strategy for health. If seeking a treatment, they will be directed to their primary care.

2-Week Washout (Pre-intervention Activities): To ensure participants have a stable level of dietary influence on the gut microbiota, participants will be asked to avoid consumption of fiber-rich and anthocyanin-rich foods (i.e., washout period) for the two weeks prior to their baseline visit. Additionally, the week before baseline participants will be asked to fill a 3-day diet record to estimate nutrient intake. As a part of the parent study, the participants will be wearing an accelerometer to measure physical activity, which will be done for the remainder of the study.

Baseline Visit (~30 minutes): At the baseline visit, participants will be asked to turn in their 3-day diet records. Participants will also be asked to collect a fecal sample as is, in a sterile collection tube without any preservation medium that will be provided to participants. Participants will temporarily store the self-collected fecal sample in their own freezer (-17°C), and then transported to the lab at HSL for sample processing and long-term storage until analysis. Other questionnaire based assessments will be administered (e.g., depressive symptom severity, positive and negative affect, suicidal ideation, relevant symptom assessment).

3-Day Diet Records: Diet records (consisting of 2 weekdays and 1 weekend) will be reviewed by research staff for accuracy and completeness. Records will be entered into a dietary analysis program (e.g., Nutrition Data System for Research) to estimate dietary intake of nutrients.

Center for Epidemiological Studies Depression Scale (CES-D) and CESD-revised (CESD-R): Depressive symptoms will be assessed by the original CES-D⁵⁸ and the CESD-R,⁵⁹ which are validated questionnaires of questions regarding feelings of depression, worthlessness, loneliness, energy level, and fear. The original CES-D questionnaire is a validated 20-item assessment. It was more recently revised to the CESD-R, which changes some of the items to ask about symptoms that are more consistent with the updated Diagnostic and Statistical Manual of Mental Disorder-5 criteria for major depression. We will implement both questionnaires since the original CES-D is most widely used in the literature and due to the high internal consistency ($r=0.90$) and a test-retest reliability of 0.51 of the CESD-R.⁶¹

Relevant Symptoms: Information on relevant symptoms including gastrointestinal distress, appetite, pain etc, will be collected by self-report. Symptoms of anxiety and sleep will also be evaluated by self-report and/or validated measures.

Positive and Negative Affect: The Positive Affect Negative Affect Scale (PANAS) is a validated questionnaire that assesses two of the most prominent dimensions of emotional experience: positive and negative affect. The questionnaire is a 20 item assessment that consists of 10 items that evaluate positive affect and an additional 10 items that evaluate negative affect.⁶²

Week 4 and Week 8 Mid-point Visit (~30 minutes): The Week 4 and Week 8 Mid-point Visit questionnaire based assessments will be administered (e.g., depressive symptom severity, suicidal ideation, relevant symptom assessment, positive/negative affect). We will also measure compliance.

Compliance: Compliance with our dietary intervention will be evaluated throughout the study. Participants will be asked to keep all of their used powder packets. At the study visit, participants will return all unused and used powder packets to estimate number of intended doses that were consumed.

Week 12 Final Follow-up Visit (~30 minutes): At the follow-up visit, participants will be asked to turn in their 3-day diet records and repeat the questionnaires/assessments that were assessed at baseline visit. Participants will also be asked to collect another fecal sample as is, in a sterile collection tube without any preservation medium that will be provided to participants. Participants will temporarily store the self-collected fecal sample in their own freezer (-17°C), and then transported to the lab at HSL for sample processing and long-term storage until analysis. Dietary compliance will also be estimated as previously described.

5.3 Dietary Intervention

The duration of this study will be a total of 14 weeks. The first two weeks will require participants to avoid eating fiber- and anthocyanin-rich foods.

Individuals will then be randomized to either the intervention or the control group. This is a double-blinded study, so the study staff not the participant will know what powder the participants are assigned to. Those randomized to the intervention group will be asked to consume approximately 48 g of freeze-dried blueberry powder as a source of ~8 g of fiber and 600 mg of anthocyanins. The proposed dose of 48 g of freeze-dried blueberry powder is equivalent to approximately 2 cups of whole blueberries. Individuals randomized to the control group will be asked to consume approximately 48 g of a nutritionally matched placebo powder that is devoid of anthocyanins and fiber.

The powders will be individually packaged in 24 g amounts. Participants will be instructed to consume their respective powder, mixed in an 8 fl oz glass of water twice per day for 12 weeks. They will be asked to consume 24 g in the morning and 24 g in the afternoon. Given that intervention and control products are regularly consumed, we do not anticipate any toxicities.

6.1 Statistical Analysis

All analyses will be performed by intent to treat, and further evaluated per protocol. As a first step, we will assess distribution characteristics of the primary and secondary outcomes. Where appropriate, transformation of variables to combat skew or other irregularities will be employed. Participant characteristics will be summarized using means, medians, standard deviations, interquartile regions and ranges for continuous variables and sample counts and proportions generated for discrete characteristics. Comparability of treatment arms will be assessed on potentially confounding characteristics using tabular and graphical methods.

6.2 Aim Statistical Methods and Power

Aim 1 Hypothesis: The abundance of microbes that produce SCFA increase after 12 weeks of dietary fiber and anthocyanin supplementation compared to placebo. **Aim 1 Analysis:** To determine taxa and pathways that differ significantly by treatment (blueberry vs. placebo powder), multivariate analyses that accounts for covariates will be carried out using MaAsLin2⁶³ (Multivariate Analysis by Linear Models). MaAsLin2 performs a mixed-effects linear regression of individual log-transformed microbial features (response) on categorical or continuous factors (explanatory variables). A random effects model will be used for repeated measures (i.e., longitudinal data). Linear models will be constructed to assess each feature independently, and adjusted for false discovery using Benjamini-Hochberg FDR. The output of MaAsLin will reveal whether cohort participants with different dietary exposures also differ in relative abundance of a particular bacterial species or pathway in the gut. **Aim 1 Expected Results/Power:** With our proposed sample size of 20/group, we anticipate power 0.95 to detect a 0.314-unit difference in common taxa (~14310 sequences and 0.0954 relative abundance at 5% read usage rate), and a 0.122-unit difference in rare taxa (~2222 sequences and 0.0148 relative abundance at 5% read usage rate) collected at the 2 time points. Approximating as above, the corresponding detection limit for 250 pathways is power 0.95 for a 0.0013-unit difference (1282 sequences at a 33% read usage rate). We assumed we will observe 250 pathways.

Aim 2 Hypothesis: The fecal SCFA's increase after 12 weeks of dietary fiber and anthocyanin supplementation compared to placebo. **Aim 2 Analysis:** Since butyrate is implicated as the gut-derived metabolite important for depression,³⁰ we will focus on the change in fecal butyrate, but others SCFA and combinations will be explored. Change in fecal butyrate will be calculated between baseline and the final 12 week follow-up. Distribution of change will be summarized using sample quantities and kernel density estimates. We will develop 80% confidence interval estimates of inter- and intra- individual variation (i.e., standard deviation) of change in fecal butyrate, the upper limit will be used to estimate sample size calculations for a subsequent clinical trial. Formal inference and estimation of treatment effects will use a Student's t-test to compare mean change in fecal butyrate in the intervention group compared to placebo. **Aim 2 Expected Results/Power:** A 12 week intervention in non-depressed older adults supplementing usual diet with prebiotic fiber, report mean percent of fecal butyrate concentration increased by 0.4%.⁶⁴ Assuming standard deviation of mean percent change of fecal butyrate = 0.32% and an alpha=0.05, a sample size of 20/group is required to detect a 0.3% change in fecal butyrate.

Aim 3 Hypothesis: Depressive symptom severity (evaluated by CES-D) declines after 12 weeks of dietary fiber and anthocyanin supplementation compared to placebo. **Aim 3 Analysis:** Change in depressive symptom severity (CES-D) will be calculated between baseline and the final 12 week follow-up (we will consider change between baseline and visits at week 4 and 8). The same analyses described for Aim 2, will be implemented for Aim 3. **Aim 3 Expected Results/Power:** Other lifestyle interventions, including dietary strategies, that were designed to reduce depressive symptoms report between a 2-4 point reduction in CES-D scores.⁶⁵⁻⁶⁷ Assuming standard deviation of change of depressive symptoms = 3.5 estimated from other lifestyle interventions and an alpha=0.05, a sample size of 20/group is needed to detect a 2 point reduction in CES-D scores.

CHAPTER 7 DATA MANAGEMENT AND QUALITY

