3.5 Study Endpoints

The primary outcomes of this study are:

- 1) **Abundance of microbes that produce SCFA** (e.g., *Bifidobacteria*, *Eubacterium*, and *Clostridium*^{56,57}) will be evaluated by whole genome sequencing (WGS). WGS will be performed in fecal samples before and after the 12 week intervention to obtain a holistic representation of the microbes in the gut and to confirm that the blueberry powder interacts with the gut microbiota WGS was chosen because it enables identification of microbes down to the specific species or strain of bacteria whereas other methods can only identify the genus level. Also, WGS tends to be less biased compared to 16S rRNA sequencing. A reputable lab (e.g., Microbial Omics Core at the Broad Institute) will perform the DNA extraction from fecal samples and whole genome sequence library construction and sequencing. Then the Fastq sequences will be processed and analyzed by a reputable lab (e.g., the Harvard Chan Microbiome Analysis Core).
- 2) **Fecal SCFA** will be measured by a reputable lab (e.g., West Coast Metabolomics Center at University of California Davis). Following sample preparation outlined in §5.2, a biphasic extraction will be performed to extract the SCFA from the fecal samples. SCFA will be separated and identified using gas chromatography mass spectrometry. Internal standards and an external curve will be used to calculate the concentration of SCFA in each sample (acetate, propionate, and butyrate).
- 3) **Depressive symptom severity** will be assessed by the original CES-D⁵⁸ and the CESD-R,⁵⁹ which are validated questionnaires of questions regarding feelings of depression, worthlessness, loneliness, energy level, and fear. See §5.2 for more information.

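### Aim 1 does not name the model term that tests its hypothesis; if it is the treatment main effect over both visits, the estimate is half the week-12 effect

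*Combined protocol and SAP*

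**What the plan says.** All of the following is in section 6.2 (Aim 1) unless noted.

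- **Hypothesis:** "The abundance of microbes that produce SCFA increase after 12 weeks of dietary fiber and anthocyanin supplementation compared to placebo". This is a between-arm difference in change or, given randomisation, in week-12 level.
- **Purpose of the test:** "To determine taxa and pathways that differ significantly by treatment (blueberry vs. placebo powder"). Covariates are to be accounted for but are not listed.
- **Model:** MaAsLin2 on log-transformed features, one feature at a time, with Benjamini-Hochberg adjustment. On the repeated samples: "A random effects model will be used for repeated measures (i.e., longitudinal data").
- **Reading of the output:** "whether cohort participants with different dietary exposures also differ in relative abundance of a particular bacterial species".
- **Sampling** (section 3.5): "WGS will be performed in fecal samples before and after the 12 week intervention". The schedule in section 5.2 confirms stool at baseline and week 12 only.
- **Power:** "With our proposed sample size of 20/group, we anticipate power 0.95 to detect a 0.314-unit difference in common taxa". The rare-taxa figure follows, ending "0.0148 relative abundance at 5% read usage rate) collected at the 2 time points", and then "the corresponding detection limit for 250 pathways is power 0.95 for a 0.0013-unit difference".

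The Aim 2 analysis, which Aim 3 adopts, calculates change from baseline to week 12 and compares mean change between arms. Aim 1 has a parallel hypothesis but no equivalent statement.

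**The concern.** The sentence that introduces the test and the sentence that interprets its output both describe a between-arm difference in abundance. Neither describes a difference in change. Combined with a repeated-measures model over two samples, the literal implementation is treatment as a fixed effect plus a participant random effect.

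In that model the treatment coefficient is the arm difference averaged over the two visits. Participants take no powder before baseline (section 5.3), so randomisation makes the expected baseline difference zero. The average is therefore diluted, and any chance imbalance at baseline feeds into it.

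Microbial abundance is listed among the primary outcomes in section 3.5 and as secondary in section 5.4, and section 8.6 says that later trials will be designed from this study's results. A diluted estimate would understate the microbial response passed on to that work, and a real response would be more likely to be missed.

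**Working it through.** **1. What can be reproduced.** The read counts are consistent with one another: 14310 / 0.0954 = 150,000 and 2222 / 0.0148 ≈ 150,000 reads, both about 3.0 million at 5% usage; 1282 / 0.0013 at 33% usage also gives about 3.0 million. The power of 0.95 cannot be reproduced, because Aim 1 gives no SD, alpha, sidedness, FDR threshold, within-person correlation or powered contrast. Solving backwards at an assumed two-sided 0.05 (normal approximation), SD = difference / [(1.960 + 1.645) × √(2/20)], so the SD of the analysed contrast would have to be 0.275 (common taxa), 0.107 (rare taxa) or 0.00114 (pathways). The plan offers nothing to compare these with.

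**2. Set-up for the conditional check.** From the plan: n = 20 per group and two visits. Assumed: equal variance σ² at both visits, correlation ρ, effect δ at week 12 only, two-sided 0.05 before FDR adjustment.

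| Contrast | Estimates | Standard error ÷ [σ√(2/n)] |
|---|---|---|
| Treatment main effect, both visits | δ/2 | √((1+ρ)/2) |
| Week 12 only | δ | 1 |
| Change, or ordinary treatment-by-visit | δ | √(2(1−ρ)) |
| Week 12 adjusted for baseline | δ | √(1−ρ²) |

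Under the main effect, the plan's differences of 0.314, 0.122 and 0.0013 would have expected estimates of 0.157, 0.061 and 0.00065.

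**3. Power of the main effect, given 0.95 for another contrast.** Power of 0.95 requires a signal-to-error ratio of 1.960 + 1.645 = 3.605. The main effect's ratio is 3.605 multiplied by a factor, and power ≈ Φ(ratio − 1.960).

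| 0.95 calibrated to | Factor | ρ=0 | 0.3 | 0.5 | 0.7 | 0.8 |
|---|---|---|---|---|---|---|
| Week 12 adjusted for baseline | √((1−ρ)/2) | 0.72 | 0.57 | 0.44 | 0.29 | 0.21 |
| Week 12 only | 1/√(2(1+ρ)) | 0.72 | 0.61 | 0.55 | 0.50 | 0.48 |
| Change | √((1−ρ)/(1+ρ)) | 0.95 | 0.75 | 0.55 | 0.33 | 0.22 |

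Example, first row at ρ = 0.5: factor √0.25 = 0.5; ratio 1.802; Φ(−0.158) = 0.44. A noncentral t with 38 df agrees with every entry to within about 0.001.

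If 0.95 was calibrated to the two-visit average but with the full δ as its effect, power is 0.44 at any ρ.

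**4. Simulation check.** In 300 mixed-model replicates (ρ = 0.5, 20 per group, true effect 1.14 SD):

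| Tested term | Mean estimate | Power |
|---|---|---|
| Main effect over both visits | 0.56 | 0.54 |
| Treatment-by-visit | 1.12 | 0.94 |
| Exposure coded zero at baseline (common baseline mean) | 1.13 | 0.98 |

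**5. Which contrast is best.** For an assumed effect of 0.9 SD at ρ = 0.5 (noncentral t, 38 df), the ratios are 0.9/(0.866 × 0.316) = 3.29 for baseline-adjusted week 12, 0.9/(1 × 0.316) = 2.85 for change, and 0.45/(0.866 × 0.316) = 1.64 for the main effect. Power is 0.89, 0.79 and 0.36.

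**The case against.** The strongest reply is that the plan never writes out a fixed-effects formula. The words about differing by treatment open a statement of purpose and do not identify a coefficient; a treatment-by-visit test also finds features that differ by treatment. The hypothesis just before it concerns a 12-week increase against placebo, and the analysis can be read as serving it. At baseline the arms do not yet have different study exposures, so exposure coded by visit is a fair reading and recovers the full effect. The unlisted covariates might include visit or baseline abundance. Aims 2 and 3 show that the team analyses before-and-after data as change.

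This stands as far as it goes. A reader might infer that the plan definitely halves the effect, that the stated 0.95 is wrong, or that the pilot will report a false null. The documents support none of these. The halving belongs to the literal reading, which is not the only one. The 0.95 is not tied to any contrast, and if it was calibrated to change at low correlation the loss is small or nil (0.95 at ρ = 0, 0.75 at 0.3). A false null would also require a true effect, and lower power makes a miss more likely, not certain.

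The reply does not supply the missing term. The only contrast named for Aim 1 is a between-arm difference, in a model that appears to include a pre-treatment response.

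**Conclusion.** The concern holds as a specification gap with a conditional consequence. Aim 1 does not say which term tests its hypothesis. If the treatment main effect over both visits is used, the expected estimate is exactly half the week-12 effect, given no true baseline difference. The accompanying power loss is illustrative only: main-effect power is about 0.57 to 0.29 for correlations of 0.3 to 0.7 if 0.95 belongs to a baseline-adjusted week-12 analysis, 0.72 to 0.48 for correlations of 0 to 0.8 if it belongs to week 12 alone, and 0.95 to 0.22 over that same range if it belongs to change. All of these assume equal variances and two-sided 0.05; the plan instead applies an FDR procedure at an unstated level. A treatment-by-visit term, or exposure coded zero at baseline, avoids the halving. Naming the baseline-adjusted contrast is worthwhile even if the team intended treatment-by-visit, because under the same assumptions it is also the more powerful of those two (0.89 against 0.79 in the example).

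**What to change.** In section 6.2, Aim 1:

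- State that the test is the treatment coefficient in a model of week-12 log-abundance adjusted for the same feature's baseline log-abundance. The alternative is the treatment-by-visit term in the random-intercept model with a common baseline mean for both arms.
- State that the treatment main effect over both visits is not the test.
- Restate the 0.95 power for the chosen contrast, with its SD, baseline-to-week-12 correlation and FDR level.

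The cost is a changed model formula and a restated power basis. Baseline stool samples are already planned, so no new data, visits or participants are needed.

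### Aim 1's 0.95 power is stated in an unnamed unit that matches arcsine-square-root abundance, but the planned test is on log abundance, so 0.95 is not power for that test

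*Combined protocol and SAP*

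**What the plan says.** All the relevant text is in section 6.2 of the combined protocol and SAP.

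- **Planned test (Aim 1 Analysis).** MaAsLin2 "performs a mixed-effects linear regression of individual log-transformed microbial features (response"), with random effects for the repeated measures. Each feature is tested separately and "adjusted for false discovery using Benjamini-Hochberg FDR".
- **Power for taxa.** "With our proposed sample size of 20/group, we anticipate power 0.95 to detect a 0.314-unit difference in common taxa". The common-taxa limit reads in full "0.314-unit difference in common taxa (~14310 sequences and 0.0954 relative abundance at 5% read usage rate"), and the rare-taxa limit is a "0.122-unit difference in rare taxa (~2222 sequences and 0.0148 relative abundance at 5% read usage rate").
- **Power for pathways.** Said to be approximated in the same way: "the corresponding detection limit for 250 pathways is power 0.95 for a 0.0013-unit difference (1282 sequences at a 33% read usage rate").
- **Not given for Aim 1.** The unit, the SD, alpha, the FDR level and the number of taxa tested. For pathways, 250 features are assumed.
- **Given for the other aims.** Aim 3 states its inputs: "Assuming standard deviation of change of depressive symptoms = 3.5 estimated from other lifestyle interventions and an alpha=0.05". Aim 2 likewise gives an SD (0.32%) and an alpha (0.05).

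No section mentions an arcsine transformation. Section 6.1 allows variables to be transformed where this is needed, without naming a transformation.

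**The concern.** Power belongs to a particular test on a particular scale. A difference on a log scale is a ratio of abundances. It cannot equal a single absolute abundance such as 0.0954 unless a reference abundance is given, and none is. So the power sentence does not describe the log-scale model even before its unit is identified.

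This sentence is the plan's only statement of what Aim 1 can detect with 20 per group. A reader faced with a null Aim 1 result would want to know which fold difference between blueberry and placebo that result makes unlikely. The plan does not allow this to be worked out, yet a figure of 0.95 suggests that large effects have been all but excluded.

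**Working it through.** **1. Identify the unit.** Inputs from section 6.2: 0.314 paired with 0.0954, and 0.122 paired with 0.0148. Candidate transformations of the printed abundances:

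| Transformation | p = 0.0954 (stated 0.314) | p = 0.0148 (stated 0.122) |
|---|---|---|
| arcsin(√p) | 0.3140 | 0.1220 |
| √p | 0.3089 | 0.1217 |
| 2·arcsin(√p) | 0.628 | 0.244 |
| ln p | −2.35 | −4.21 |
| log10 p | −1.02 | −1.83 |
| ln(1 + p) | 0.091 | 0.015 |

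Only arcsin(√p) reproduces both printed values.

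**2. Check against the sequence counts.**

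- 14310 / 0.0954 = 150,000 usable reads. At 5% usage, 150,000 / 0.05 = 3.0 million reads in total.
- 2222 / 0.0148 ≈ 150,135 usable reads, again about 3.0 million in total.
- Forward: sin²(0.314) × 150,000 = 14,310 and sin²(0.122) × 150,000 = 2,221.5, which rounds to 2,222.

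The plan's taxa figures are thus reproduced exactly on the arcsine-square-root scale. The printed 0.0954 and 0.0148 are the abundances reached by shifts of 0.314 and 0.122 from a reference of zero, where a fold difference is undefined.

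**3. Translate to fold differences.** With reference abundance p and shift d, the other arm has q = sin²(arcsin(√p) + d), and the fold difference is q/p. The reference values below are assumptions, because the documents give none.

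| d | p | q | q/p |
|---|---|---|---|
| 0.314 | 1% | 16.2% | 16.2 |
| 0.314 | 5% | 26.4% | 5.3 |
| 0.314 | 10% | 35.3% | 3.5 |
| 0.314 | 20% | 49.2% | 2.5 |
| 0.122 | 0.1% | 2.34% | 23.4 |
| 0.122 | 0.5% | 3.67% | 7.3 |
| 0.122 | 1% | 4.86% | 4.9 |

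One arcsine shift therefore corresponds to many different log-scale effects.

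**4. Pathways.** Assuming the same 3.0 million reads, 33% usage gives 990,000 usable reads.

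- 1282 / 990,000 = 0.001295, so the stated 0.0013 is an untransformed proportion.
- In the taxa unit the same count would be arcsin(√0.001295) = 0.036.
- Conversely, 0.0013 in the taxa unit would be sin²(0.0013) × 990,000 ≈ 1.7 sequences, not 1282.

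**5. Try to reproduce the 0.95.** This cannot be done from the plan, which lacks the SD and the error level. It can only be back-solved. For a two-group comparison at two-sided alpha 0.05 (assumed), normal approximation:

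- d/SD = (1.960 + 1.645) × √(2/20) = 1.140.
- The implied SD is 0.314 / 1.140 = 0.275 for common taxa and 0.122 / 1.140 = 0.107 for rare taxa, both on the unnamed scale.

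**6. What the log scale would need.** Under the same assumptions and with no FDR adjustment, the fold difference detectable with power 0.95 is exp(1.140 × SD), where SD is on the natural-log scale. This gives 1.77 at SD 0.5, 3.1 at SD 1.0 and 9.8 at SD 2.0. The documents do not say which SD applies.

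**The case against.** **The unit is inferred.** The plan never names the arcsine scale, and its wording is that of an anticipated approximation. The fault might therefore be an undisclosed approximation rather than a wrong power. It is true that the scale is inferred and that true power could lie on either side of 0.95. But two abundances and two counts agree with one transformation, and a log difference could not equal an absolute abundance in any case.

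**The fold table is illustrative.** The reference abundances are not the plan's. With two time points the difference may also be one of change between arms, in which case q/p is not the relevant quantity. Both points stand. The table shows that the conversion is not fixed. It does not show what Aim 1 can detect.

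**The pathway point assumes a read depth.** This also stands. The 3.0 million is implied by the taxa figures and carried over to pathways.

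**It is a pilot.** The 40 participants come from the parent trial (sections 3.2 and 3.4), the aim is preliminary evidence (section 3.1), and definitive powering is left to later trials (section 8.6). A null result would be read mainly from estimates and intervals. This limits the consequence but does not make the sentence correct. Microbial abundance is listed as primary in section 3.5 (secondary in section 5.4), and Aim 1 carries a directional hypothesis.

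**Conclusion.** The concern holds. The 0.95 is attached to a different scale from the planned log-scale, FDR-adjusted model, and the taxa and pathway limits appear to be in two unlabelled units. The taxa arithmetic is exact on its own scale, so this is a mismatch between the power statement and the analysis rather than a miscalculated effect size.

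No corrected power can be given, and the plan is not shown to be over- or underpowered. The identification of the arcsine scale rests on the numerical match, and the pathway finding rests on a common read depth. The consequence is confined to how Aim 1 results are interpreted. The text should be corrected, but recruitment, procedures and analysis are unaffected.

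**What to change.** Keep the log-scale analysis, and do not change its transformation to suit the power sentence. In section 6.2, restate the Aim 1 limits for both taxa and pathways, in one unit, as blueberry-versus-placebo fold differences on the log scale. Give the assumed log-scale SD and its source, the FDR level, and the number of features tested (250 is stated for pathways; a number is needed for taxa).

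If no log-scale SD is available, delete the 0.95 and describe Aim 1 as exploratory estimation.

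The cost is a short recalculation and possibly the loss of a stated power figure. Sample size, procedures and the planned test stay as they are.
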